4.4. Duration of Treatment and Subject Participation

Screening is up to 28 days (4 weeks), the double-blind, vehicle-controlled, treatment period is 24 weeks, the continued double-blind treatment period is 28 weeks (52 weeks cumulative double-blind), the optional open-label extension treatment is 104 weeks, and safety follow-up is 24 weeks. Total duration is up to 184 weeks.

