5.5.2. Withdrawal Procedures

In the event that the decision is made to permanently discontinue the study drug, the subject will be withdrawn from the study, and the EOT visit should be conducted. Reasonable efforts should be made to have the subject return for a follow-up visit. These visits are described in Section 6. The last date of the last dose of study drug and the reason for subject withdrawal will be recorded in the eCRF.

[figure not shown]
If a subject is withdrawn from the study:

[figure not shown]
- The study monitor or sponsor must be notified.
- The reason(s) for withdrawal must be documented in the subject's medical record and in the eCRF.
- The EOT visit should be performed.
- The date of the EOT visit should be recorded in the IRT.
- Subjects must be followed for safety until the time of the follow-up visit or until study drug-related toxicities resolve, return to baseline, or are deemed irreversible, whichever is longest.

If the subject discontinues study treatment and actively withdraws consent for collection of follow-up data (safety follow-up or disease assessment), then no additional data collection should occur; however, subjects will have the option of withdrawing consent for study treatment but continuing in the follow-up period of the study for safety/efficacy assessments.

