9.4.1.2. Primary Efficacy Analyses

For the primary analysis, comparisons between each active group and vehicle based on F-VASI50 at Week 24 will be performed in the ITT population, with a logistic regression with treatment groups and stratification factor of baseline age. Exact logistic regression ([Mehta and Patel 1995](#)) will be used for all of the comparisons if any of the dose levels has an expected cell count less than 5. The proportions, along with unadjusted p-values and 95% confidence intervals, will be reported. All nonresponders, as well as all subjects who discontinue study treatment at any time before the timepoint of interest or discontinue from the study for any reason, will be defined as nonresponders for the nonresponder imputation analysis.

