#### 2. STUDY INFORMATION, OBJECTIVES, AND ENDPOINTS

#### 2.1. Protocol and Case Report Form Version

This SAP is based on INCB 18424-211 Protocol Amendment 1 dated 17 MAY 2017 and CRFs approved 06 JUN 2017. Unless superseded by an amendment, this SAP will be effective for all subsequent Protocol amendments and eCRF versions.

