#### 4.2.4. Handling of Missing and Incomplete Data

For response endpoints, all nonresponders, as well as all subjects who discontinue study treatment at any time before the timepoint of interest or discontinue from the study for any reason will be defined as nonresponders for NRI analysis.

For other endpoints, missing observations will be handled as detailed in the specific sections addressing each analysis.

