#### 7.3.1. Primary Efficacy Analysis

The primary endpoint is the proportion of subjects treated with INCB018424 cream who achieve an F-VASI50 at Week 24 compared with subjects treated with vehicle cream. The comparison of the primary endpoint will be performed in the ITT population for the superiority of either INCB018424 cream 1.5% BID or 1.5% QD versus vehicle cream using the Bonferroni-Holm procedure at an overall 2-sided  $\alpha=0.05$  level. The graphical approach that controls the Type I error rate can be found in Figure 2. The percentage of subjects achieving an F-VASI50 response at Week 24 will be analyzed by logistic regression using stratification factor of randomization (ie, age  $\leq 30$  or > 30 years) and treatment group as predictors. Exact logistic regression (Mehta and Patel 1995) will be used for all of the comparisons if any of the dose levels has an expected cell count less than 5. The proportions, along with unadjusted p-values and 95% confidence intervals, will be reported. All nonresponders in the DB period, as well as all subjects who discontinue study treatment at any time before the timepoint of interest or discontinue from the study for any reason, will be defined as nonresponders for the NRI analysis.

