#### 7.4.1. Efficacy Analysis for Key Secondary Endpoints

The percentage of F-PhGVA responders at Week 24, as well as the percentage of T-VASI50 responders at Week 52, will be analyzed using similar logistic regression as specified in the primary efficacy analysis. The NRI rule for missing data is the same as in F-VASI50. The graphical approach as specified in Figure 2 will be used to control the family-wise error rate.

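### The nonresponder rule puts a time limit on stopping treatment but not on leaving the study, so read literally an observed Week 24 response could be recoded after a later exit

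*SAP*

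**What the plan says.** SAP 4.2.4 gives the general rule for response endpoints. Besides observed nonresponders, those subjects that "discontinue study treatment at any time before the timepoint of interest or discontinue from the study for any reason will be defined as nonresponders" count as failures. SAP 7.3.1 repeats it for F-VASI50 at Week 24, covering those "who discontinue study treatment at any time before the timepoint of interest or discontinue from the study for any reason, will be defined as nonresponders". Protocol 9.4.1.2 uses the same construction, ending "or discontinue from the study for any reason, will be defined as nonresponders for the nonresponder imputation analysis". SAP 7.4.1 carries the rule to F-PhGVA response at Week 24 and T-VASI50 at Week 52: "The NRI rule for missing data is the same as in F-VASI50".

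Three other provisions bear on how it would operate:

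- Protocol 4.4, on participation: "Total duration is up to 184 weeks". SAP 2.1 says that "this SAP will be effective for all subsequent Protocol amendments and eCRF versions", so the current protocol's timeline applies although the SAP describes a 52-week open-label period.
- Protocol 5.5.2, on stopping drug: "In the event that the decision is made to permanently discontinue the study drug, the subject will be withdrawn from the study". The same section lets a subject who withdraws consent for treatment stay in follow-up.
- Protocol 4.1 and 6.3 unblind the sponsor's primary endpoint team after Week 24. SAP 9 defines data cutoffs for the two interim analyses; neither document states one for the primary analysis.

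**The concern.** The rule has two conditions joined by *or*. Stopping treatment counts only if it happens before the analysis visit. Leaving the study counts whenever it happens. A subject assessed on treatment at Week 24, with at least 50% improvement in F-VASI, who leaves the study at Week 30 meets the second condition and would be recoded as a Week 24 failure.

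Two consequences follow. A measured primary endpoint is overwritten by an event that came after it. The Week 24 responder count also depends on when the program is run: the same subject is a responder at an early cut and a nonresponder at a later one. A programmer following the sentence and a programmer following its likely intent would report different counts. If the choice is left until the primary endpoint team is unblinded, it is made with the results known.

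Protocol 5.5.2 adds a route. A subject who stops drug after Week 24 is exempt under the first condition, but if that leads to withdrawal from the study, the second condition catches the same subject.

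**Working it through.** **Text.** In all three statements of the rule, the time limit sits inside the treatment clause and the study clause stands outside it. In SAP 7.3.1 the reference to the double-blind period qualifies the observed nonresponders, not the discontinuations. No other passage puts a time limit on the study clause.

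**Time after Week 24.** Protocol 4.4: 4 + 24 + 28 + 104 + 24 = 184 weeks, of which 28 + 104 + 24 = 156 come after Week 24. Under the SAP's own older schema: 28 + 52 + 97/7 ≈ 94 weeks after Week 24. The 28 weeks from Week 24 to Week 52 are double-blind in both.

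**The plan's power figure.** Inputs from Protocol 9.2 and SAP 3.3: response rates 55% (1.5% BID), 50% (1.5% QD) and 5% (vehicle); two-sided alpha 0.025; Fisher's exact test; 25 per group. Exact power is the sum, over all pairs of responder counts with Fisher p ≤ 0.025, of Bin(a; n, p_active) × Bin(b; n, p_vehicle). With n = 25 this gives 95.9% and 91.5%, which agrees with the stated figure of more than 90%.

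**Effect of the literal rule.** Use 30 randomized per arm, since the analysis is ITT. Let w be the share of Week 24 responders who later leave the study. The documents give no value for w, so a range is shown. The recoded rate is p × (1 − w).

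| w (equal in all arms) | Rates: BID / QD / vehicle | Power: BID / QD vs vehicle |
|---|---|---|
| 0% | 55% / 50% / 5% | 98.7% / 96.4% |
| 10% | 49.5% / 45% / 4.5% | 96.7% / 92.8% |
| 20% | 44% / 40% / 4% | 92.9% / 86.8% |
| 30% | 38.5% / 35% / 3.5% | 86.0% / 77.8% |

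One recoded responder moves an arm by 1/30 = 3.3 percentage points. At w = 10% the 1.5% BID arm loses 30 × 0.55 × 0.10 = 1.65 responders on average.

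**If the planned 20% dropout before Week 24 also counts as nonresponse**, the rates become p × 0.8 × (1 − w). Power is 92.9% / 86.8% at w = 0 and 80.0% / 71.0% at w = 20%. Only the drop between these two pairs is due to the wording.

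**Unequal later withdrawal** (also assumed). With w = 20% in the active arms and 0% in vehicle, power is 90.1% / 82.7%. With 0% in active and 20% in vehicle, it is 99.2% / 97.6%. The comparison could therefore shift in either direction.

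**The case against.** The strongest reply is that context supplies the missing limit. The rule sits under a heading on missing and incomplete data, and SAP 7.4.1 calls it a missing-data rule; a subject assessed at Week 24 has no missing Week 24 value. SAP 7.2.1 defines F-VASI50 by the improvement achieved, with no reference to later events. SAP 9 treats leaving the study and stopping treatment alike, as alternatives to completing a visit. This makes it likely that both conditions were meant to be limited. It does not change the wording of the rule, which is what will be programmed.

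A second reply concerns the exposed period. SAP 5.2 presents double-blind and open-label results separately, and SAP 7.2.1 and 7.4 place the primary and secondary analyses in the double-blind period. A reader might infer from the 184-week duration that any exit up to the end of follow-up would alter the Week 24 result. The documents do not support putting it that strongly: open-label or follow-up exits are less likely to feed the double-blind tables, though no passage excludes them. For the same reason T-VASI50 at Week 52 is much less exposed, because the double-blind period ends at that visit. Exits between Week 24 and Week 52 remain exposed for both Week 24 endpoints.

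A third reply concerns frequency. A reader might infer from Protocol 5.5.2 that everyone who stops drug leaves the study and that recoding would be common. The same section offers continued follow-up after consent for treatment is withdrawn, Protocol 6.3 encourages follow-up visits, and no withdrawal rate after Week 24 is given. Neither inference is supported. At w = 10% both comparisons also stay above the planned 90% power.

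**Conclusion.** The rule is wrong as written. It time-limits one kind of discontinuation and not the other, and followed literally it replaces an observed Week 24 response with a failure because of a later event. This was probably not intended, but the text does not prevent it, and it governs the primary endpoint.

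The size cannot be taken from the documents. The only dropout figure, 20%, covers the first 24 weeks. If 10% to 30% of Week 24 responders left later, equally in every arm, power would fall from 98.7% / 96.4% to between 96.7% / 92.8% and 86.0% / 77.8%. These figures rest on the literal reading, on the assumed shares, and on Fisher's test in place of the planned logistic regression. Bias in a particular direction would need withdrawal after Week 24 to differ by arm. That is possible, since all vehicle subjects move to active drug at Week 24, but nothing in the documents shows it.

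**What to change.** Revise the sentence in SAP 4.2.4, SAP 7.3.1 and Protocol 9.4.1.2 so that the limit covers both conditions. Suggested text: *A subject is a nonresponder at a given visit if, before the assessment at that visit, the subject stopped study treatment or left the study, or if no assessment was made at that visit. Stopping treatment or leaving the study after that assessment does not change the response recorded.* SAP 7.4.1 then inherits the corrected rule by reference.

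The clause on absent assessments closes a related gap: the rule says nothing about a subject who is still on treatment and in the study but misses the visit.

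The cost is one sentence in each place, with no added data or patient burden. The change should be made before the Week 24 data are analysed unblinded. If that has already happened, the report should state which reading was programmed and how many observed responders it changed.

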#### 5. STATISTICAL METHODOLOGY

## 5.1. General Methodology

Unless otherwise noted, SAS® software (SAS Institute Inc., Cary, NC; v9 or later) will be used for the generation of all tables, graphs, and statistical analyses. Descriptive summaries for continuous variables will include, but not be limited to, the number of observations, mean,

standard deviation, median, minimum, and maximum. Descriptive summaries for categorical variables will include the number and percentage of subjects in each category.

Interim analyses are planned for this study as defined in Section 9.

## **5.2.** Treatment Groups

This is a 3-part study with a 24-week, randomized, DB, and vehicle-controlled treatment period followed by a 28-week, continued, DB treatment period (52 weeks cumulative DB), and an optional 52-week OL treatment period. Data will be summarized by treatment group based on the treatment regimen that was initially assigned or received during the DB period. The results will be summarized and presented separately for the DB period and OL period. Treatment groups are as follows:

- INCB018424 cream 1.5% BID
- INCB018424 cream 1.5% QD
- INCB018424 cream 0.5% QD
- INCB018424 cream 0.15% QD
- Vehicle cream BID

## 5.3. Analysis Populations

## **5.3.1.** Intent-to-Treat Population

All subjects who are randomized will constitute the ITT population. Treatment groups for this population will be defined according to the treatment assignment at the time of randomization regardless of the actual INCB018424 cream or vehicle cream subjects might apply during their participation in the study.

The ITT population will be used for the summary of demographics, baseline characteristics, subject disposition, and analyses of all efficacy data.

#### **5.3.2.** Per Protocol Population

Subjects in the ITT population who are considered to be sufficiently compliant with the Protocol will comprise the PP population.

The PP population will be used in the supportive sensitivity analyses of the primary efficacy endpoints.

#### **5.3.3.** Safety Evaluable Population

All randomized subjects who applied at least 1 dose of INCB018424 cream or vehicle cream will constitute the safety evaluable population. Treatment groups for this population will be determined according to the actual treatment the subject received on Day 1 regardless of assigned study drug treatment.

The safety evaluable population will be used for all safety analyses.

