9. STATISTICS

9.1. Study Populations

The ITT population includes all randomized subjects. Treatment groups for this population will be defined according to the treatment assignment at randomization.

The per protocol population includes randomized subjects who are considered to be sufficiently compliant with the Protocol.

The safety evaluable population includes all subjects who applied at least 1 dose of study drug. Treatment groups for this population will be determined according to the actual treatment the subject received on Day 1.

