#### 3. STUDY DESIGN

This is a 3-part, randomized, DB, and vehicle-controlled study in subjects with vitiligo who have depigmented areas including at least 0.5% of the T-BSA on the face and at least 3% of the T-BSA on nonfacial areas as determined by the palmar (or handprint- palm plus 5 digits) method. Approximately 150 subjects, aged 18 to 75 years, will be randomized to 1 of 4 dose strengths of INCB018424 cream (1.5% BID, 1.5% QD, 0.5% QD, 0.15% QD) or vehicle cream in a 1:1:1:1:1 ratio and stratified by age ( $\leq$  30 or > 30 years), with no more than 50% of the population being over 30 years of age.

Subjects will receive blinded treatment for up to 52 weeks to examine efficacy, safety, and tolerability. The 3 parts of the study include a 24-week, DB, vehicle-controlled treatment period; a 28-week, continued, DB treatment period; and a 52-week, OL extension period (see Figure 1). The primary endpoint of F-VASI50 will be evaluated at Week 24. After completion of the Week 24 assessments, subjects randomized to vehicle will be randomized to 1 of the 3 higher active treatment groups in a 1:1:1 ratio while maintaining the blind. Subjects in the INCB018424 0.15% QD group who do not achieve a  $\geq$  25% improvement from baseline on F-VASI (nonresponders of F-VASI25) will be re-randomized to 1 of the 3 higher active treatment groups while maintaining the blind. Subjects randomized to INCB018424 0.15% QD who achieve a  $\geq$  25% improvement from baseline on F-VASI will remain on the same dose until Week 52. Subjects randomized to INCB018424 1.5% BID, 1.5% QD, and 0.5% QD will remain on the same dose until Week 52.

After completion of the Week 52 assessments, subjects who continue to be eligible for the study have the opportunity to receive an additional 52 weeks of OL treatment with INCB018424 1.5% cream BID.

Figure 1: Study Design Schema

Screening		Double-Blind (		Open-Label	Follow-up
Up to 28 days		Day 1 to Week 24 a	Weeks 24 to 52	Weeks 52 to 104 b	Up to 97 days
Men and women aged 18 to 75 years with vitiligo ≥ 0.5% facial BSA and ≥ 3% nonfacial BSA	Randomization	1.5% BID	→ 1.5% BID → 1.5% QD → 0.5% QD → 0.15% QD	INCB018424 cream 1.5% BID	

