## 6.4. Exposure

For subjects in the safety population in the DB period and subjects in the OL evaluable population in the OL period, descriptive statistics will be provided by treatment group for duration of treatment, average daily dose, and total dose. Duration of treatment with INCB018424 cream or vehicle cream is defined as the number of days from Day 1 to the last record (defined in Table 2) of INCB018424 cream or vehicle cream application.

**Table 2:** Definition of Variables for Duration of Treatment

Study Period	Treatment Group a	Day 1	Last Record
--------------	------------------------------	-------	-------------

DB period	INCB018424 cream 1.5% BID 1.5% QD 0.5% QD 0.15% QD vehicle cream BID	Date of first application in DB period.	Date of last record in DB period.
OL period	INCB018424 cream 1.5% BID	Date of first application in DB period.	Date of last record in the OL period.
	INCB018424 cream 1.5% QD 0.5% QD 0.15% QD vehicle cream BID	Date of first application in OL period.	Date of last record in the OL period.

<sup>a Treatment group initially assigned or actual treatment received during the DB period.

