#### 8. SAFETY AND TOLERABILITY

Appendix A provides a list of data displays.

#### 8.1. General Considerations

Summary tables may be replaced with listings when appropriate. For instance, an AE frequency table may be replaced with a listing if it only contains a few unique PTs reported on relatively few subjects.

Unless otherwise stated, table summaries will be limited to AEs occurring within 30 days of the last administration of study drug.

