#### 8.2. Adverse Events

#### 8.2.1. Adverse Event Definitions

A TEAE is any AE either reported for the first time or worsening of a pre-existing event after first application of study drug. Analysis of AEs (as discussed below) will be limited to TEAEs, but data listings will include all AEs regardless of their timing in relation to study drug application.

Adverse events will be tabulated by MedDRA PT and SOC. Severity of AEs will be graded using the NCI CTCAE. The CTCAE v4.03 is used for this study. The CTCAE reporting guidelines and grading details are available on the Cancer Therapy Evaluation Program website.

The subset of AEs considered by the investigator to be related to study drug will be considered to be treatment-related AEs. If the investigator does not specify the relationship of the AE to study drug, the AE will be considered to be treatment-related. The incidence of AEs and treatmentrelated AEs will be tabulated. In addition, SAEs will also be tabulated.

Any missing onset date, causality, or severity must be queried for resolution. Unresolved missing causality and severity will be handled according to the following rules:

- An unresolved missing causality will be considered treatment-related.
- An unresolved missing severity will be identified as an unknown severity.

For purposes of analysis, all AEs will be considered TEAEs unless the AE can unequivocally be defined as not treatment emergent.

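### Double-blind exposure, and by natural reading adverse events, stay under the Day 1 arm after the Week 24 switch, and no visible table isolates the vehicle-controlled Weeks 0-24

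*SAP*

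**What the plan says.** **The switch.** SAP 3 states that, once the Week 24 assessments are done, "subjects randomized to vehicle will be randomized to 1 of the 3 higher active treatment groups in a 1:1:1 ratio while maintaining the blind". SAP 3 and 3.1 also re-randomize the 0.15% QD subjects who have not reached 25% improvement in F-VASI. The other three arms continue unchanged to Week 52.

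**Grouping.** SAP 5.3.3 fixes the groups for all safety analyses; they are "determined according to the actual treatment the subject received on Day 1 regardless of assigned study drug treatment". Protocol 9.1 has the same rule: "Treatment groups for this population will be determined according to the actual treatment the subject received on Day 1".

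**Periods.** SAP 5.2 joins the 24-week and 28-week parts into one DB period and adds: "The results will be summarized and presented separately for the DB period and OL period". It names five groups, all of them initial assignments.

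**Exposure.** Under SAP 6.4, "descriptive statistics will be provided by treatment group for duration of treatment, average daily dose, and total dose". In Table 2 the DB row, which includes vehicle cream BID, runs from the first DB application to "Date of last record in DB period".

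**Adverse events.** SAP 8.2.1 sets the start: "A TEAE is any AE either reported for the first time or worsening of a pre-existing event after first application of study drug". SAP 8.1 sets the end: "table summaries will be limited to AEs occurring within 30 days of the last administration of study drug". SAP 8.2.2 counts subjects by treatment group. The visible AE and exposure titles in Appendix A, under the DB heading, name no Week 24 limit.

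**The concern.** Safety and tolerability is a stated secondary objective, and Weeks 0-24 are the only time when anyone is on vehicle alone. If the DB tables run to Week 52 with columns fixed on Day 1, the vehicle column mixes 24 weeks of vehicle with up to 28 weeks of an active regimen. The 0.15% QD column mixes that dose with higher ones. An AE caused by the drug would then also build up in the vehicle column, so the contrast shrinks in the direction that hides harm.

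The plan deals with the later change of treatment differently. For arms moving to 1.5% BID in the open-label period, Tables 1 and 2 restart Day 1 at the first open-label application. Nothing comparable is set at Week 24. Disposition (SAP 6.2) is reported at both Week 24 and Week 52, but AEs and exposure are not.

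**Working it through.** **1. Length of the DB period.** SAP 5.2 gives 24 + 28 = 52 weeks, which reproduces its cumulative figure. The post-switch part is 28/52 = 53.8% for a subject who completes.

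**2. Subject-weeks in the vehicle column.** Inputs: 30 subjects per arm (Protocol synopsis) and 20% dropout in the first 24 weeks (SAP 3.3). Assumed: no dropout after Week 24. The dropout time is not given, so the 6 early leavers contribute 0, 12 or 24 weeks each.

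- Reach Week 24: 30 × 0.8 = 24.
- After the switch: 24 × 28 = 672 subject-weeks.
- Before the switch: 24 × 24 + 6 × (0, 12 or 24) = 576, 648 or 720.
- Share after the switch: 672/1248 = 53.8%, 672/1320 = 50.9%, 672/1392 = 48.3%.

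If a further 20% of the 24 left midway through Weeks 24-52 (assumed), post-switch time is 19.2 × 28 + 4.8 × 14 = 604.8 subject-weeks, and the share is 51.2%, 48.3% or 45.7%.

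**3. What the vehicle exposure row would show.** Mean duration is 1248/30 = 41.6 to 1392/30 = 46.4 weeks. The median is 52, because 24 of 30 reach Week 52. Mean vehicle-only treatment is 576/30 = 19.2 to 720/30 = 24.0 weeks.

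**4. The 0.15% QD column.** The documents give no switch rate. If 25% to 75% of completers switch (assumed), the post-switch share is 0.25 × 48.3% = 12% to 0.75 × 53.8% = 40%.

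**5. Effect on AE percentages.** The AE tables count subjects, so the share in step 2 does not measure their bias. As an illustration, take constant hazards, no dropout, one active rate, and 24-week risks *v* (vehicle) and *a* (active), all assumed:

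- Vehicle column at Week 52: 1 − (1 − v)(1 − a)^(28/24)
- Active column at Week 52: 1 − (1 − a)^(52/24)
- Difference: (a − v)(1 − a)^(28/24), against a − v at Week 24
- Relative loss: 1 − (1 − a)^(28/24), whatever the value of v

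| 24-week active risk | Loss in absolute difference |
|---|---|
| 2% | 2.3% |
| 5% | 5.8% |
| 10% | 11.6% |
| 20% | 22.9% |
| 30% | 34.0% |
| 40% | 44.9% |

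For 10% on vehicle and 30% on active, the columns read 40.6% and 53.8%: a gap of 13.2 points, where a Week 0-24 table would show 20. Ratios suffer more than differences. For 5% and 10%, the columns read 16.0% and 20.4%: the gap moves only from 5.0 to 4.4 points, but the risk ratio falls from 2.0 to 20.4/16.0 = 1.28.

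**6. What is untouched.** The Week 24 tests use data from before the switch. The Week 52 tests compare arms that do not switch. By-visit summaries through Week 24 can be read as they stand, and a Kaplan-Meier estimate at Week 24 or earlier uses no later data.

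**The case against.** **The grouping wording is loose.** SAP 5.2 and the Table 2 footnote refer to treatment initially assigned or received during the DB period. Alone, that could allow regrouping. But SAP 5.3.3 fixes Day 1 treatment for all safety analyses, and Table 2 has no post-switch row or start date.

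**The AE window is not stated.** This stands. SAP 8.1 and 8.2 set no explicit DB end, so the placement of post-switch AEs is a reading of several sections together. SAP 5.3.4 is not visible, and the Appendix A list is broken between the DB AE and vital-sign tables, so a hidden table cannot be excluded.

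**Vehicle use does not stop at Week 24.** A reader might infer that the exposure row reports more vehicle than anyone can receive. The documents do not support that. Study cream is applied twice daily from tubes labelled for morning or evening (Protocol 5.2.1 and 5.2.2), and a note to SAP Figure 1 has QD regimens use vehicle in the evening. That note is attached to the first 24 weeks, but the preserved blind implies that it continues. Subjects switched to a QD regimen would thus still apply vehicle. Only vehicle-only treatment is limited to about 24 weeks.

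**Half the person-time is not half the signal.** A reader might also carry the 48% to 54% over to AE differences. Step 5 shows why that fails: at low risks, plausible for single preferred terms, the absolute difference shrinks little.

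**There are other looks at the data.** The second interim analysis (SAP 9) reviews safety around Week 24, but on a cut defined by the first 75 subjects and with no listed table. Planned AE and drug-administration listings allow a later split, which makes repair cheap but does not prespecify it.

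**Conclusion.** The gap is real and worth closing. For exposure it follows from the text: DB duration and dose are summarized over up to 52 weeks by Day 1 treatment, and with 30 per arm and 20% dropout by Week 24, about half of the vehicle column's subject-weeks come after the switch (48% to 54% with no later dropout; down to 46% with a further 20% leaving midway). For AEs the same placement is the natural reading, but an inference. Its effect on absolute differences ranges from about 2% to 45% over assumed active risks of 2% to 40%; no AE risk comes from the documents.

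A reader might infer that efficacy conclusions are compromised as well. They are not: every confirmatory test is unaffected. The one efficacy item exposed is the optional log-rank test in SAP 7.4.2, on endpoints without multiplicity adjustment, if it compares with vehicle or 0.15% QD beyond Week 24.

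**What to change.** 1. Add AE and exposure tables for Day 1 to Week 24 by Day 1 treatment, named as the vehicle-controlled safety comparison. Cut each subject at the first application after the Week 24 assessments; for earlier leavers keep the 30-day rule of SAP 8.1. This fits SAP 5.3.3 and Protocol 9.1 as they stand, and because Appendix A describes its list as a guideline, it may need no formal amendment.
2. Summarize Weeks 24-52 AEs and exposure by the treatment received after the switch, counted from the switch date. Each vehicle sequence would hold about 24/3 = 8 subjects, so pool where columns are small; the layout is a presentation choice. This changes the grouping rule: amend SAP 5.2, 5.3.3 and 6.4 (Table 2) and align Protocol 9.1.
3. If the optional log-rank test is run against vehicle or 0.15% QD, limit it to data through the Week 24 visit. Do not censor only the switched 0.15% QD subjects, who are selected for poor response.

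The cost is a few extra tables, some with small columns, and SAP and Protocol wording. No new data are needed.
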